10.4. Appendix 4: Liver Safety: Suggested Actions and Follow-up Assessments

Selected tests may be obtained in the event of a treatment-emergent hepatic abnormality and may be required in follow-up with participants in consultation with the Lilly CRP/CRS, or that of its designee.

Hepatic Monitoring Tests

Hepatic Hematology^a	Haptoglobin^a
Hemoglobin	
Hematocrit	Hepatic Coagulation^a
RBC	Prothrombin Time
WBC	Prothrombin Time, INR
Neutrophils, segmented	
Lymphocytes	Hepatic Serologies^{a,b}
Monocytes	Hepatitis A antibody, total
Eosinophils	Hepatitis A antibody, IgM
Basophils	Hepatitis B surface antigen
Platelets	Hepatitis B surface antibody
	Hepatitis B Core antibody
Hepatic Chemistry^a	Hepatitis C antibody
Total bilirubin	Hepatitis E antibody, IgG
Direct bilirubin	Hepatitis E antibody, IgM
Alkaline phosphatase	
ALT	Anti-nuclear antibody^a
AST	Alkaline Phosphatase Isoenzymes^a
GGT	Anti-smooth muscle antibody (or anti-actin antibody)^a
CPK	

Abbreviations: ALT = alanine aminotransferase; AST = aspartate aminotransferase; CPK = creatinine phosphokinase; GGT = gamma-glutamyl transferase; Ig = immunoglobulin; INR = international normalized ratio; RBC = red blood cells; WBC = white blood cells.

^a Central laboratory. In addition, local labs may be collected at investigator's discretion.

^b Reflex/confirmation dependent on regulatory requirements and/or testing availability.

10.5. Appendix 5: Creatinine Clearance Formula

Note: This formula is to be used for calculating creatinine clearance (CrCl) from **local laboratory results only**.

Patients aged ≥ 18 years

Cockcroft-Gault prediction of CrCl from serum creatinine (1976)

For serum creatinine concentration in mg/dL:

$$\text{CrCl} = \frac{(140 - \text{age}^a) \times (\text{wt}) \times 0.85 \text{ (if female), or } \times 1.0 \text{ (if male)}}{72 \times \text{serum creatinine (mg/dL)}} \text{ (mL/min)}$$

[figure not shown]
For serum creatinine concentration in $\mu\text{mol/L}$:

$$\text{CrCl} = \frac{(140 - \text{age}^a) \times (\text{wt}) \times 0.85 \text{ (if female), or } \times 1.0 \text{ (if male)}}{0.81 \times \text{serum creatinine } (\mu\text{mol/L})} \text{ (mL/min)}$$

^a Age in years, weight (wt) in kilograms.

Source: Cockcroft and Gault 1976.

10.6. Appendix 6: Dose-Finding Algorithm of the Modified Toxicity Probability Interval Method Showing Number of Patients Treated

The number of patients dosed at a given dose level is shown in the columns (X-axis), while the number of DLTs experienced is shown in the rows (Y-axis). The rules in this figure will be used for each dose level evaluated; the patient numbers and DLTs do not carry over from cohort to cohort. By locating the intersection of the number of patients dosed and the number of DLTs, 1 of 4 predefined rules is used:

- E: Escalate the dose
- S: Stay at the same dose
- D: De-escalate the dose
- DU: De-escalate the dose due to unacceptable toxicity. The dose cannot be re-escalated to this dose level at a future point in the escalation.

For example, within a cohort:

- If 1 of 3 patients experiences a DLT, stay at the same dose (see “S” in column 3, row 1). The fourth patient must be treated at the same dose level.
- If 1 of 6 patients experiences a DLT, escalate the dose (see “E” at column 6, row 1).
- If 2 of 3 patients experience a DLT the dose to treat the next patient is de-escalated (see “D” at column 3, row 2). If 5 of 7 patients experience a DLT, the dose is determined to be unacceptably toxic and will never be used again in the trial (see “DU” at column 7, row 5).

The final MTD will be determined when all patients complete DLT evaluation. A hypothetical example for the MTD determination is shown below for illustration (based on the pre-specified parameters, number of DLTs, and number of DLT-evaluable patients).

$p_T = 0.3$, $\epsilon_1 = 0.05$, $\epsilon_2 = 0.05$, $n_{dose} = 6$, Dose level 5 is the MTD

Dose level	1	2	3	4	5	6
# of Toxicities	0	0	0	1	0	2
# of Patients Treated	1	3	3	6	3	3

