4.1.1. Dose Escalation Phase

Phase 1a (dose escalation) will assess the safety and tolerability of LY3435151 to identify a monotherapy recommended phase 2 dose (RP2D) and a combination RP2D in patients with solid tumors associated with TIL positivity:

- TNBC
- Gastric adenocarcinoma (including gastroesophageal junction)
- HNSCC
- Squamous cervical carcinoma
- High-grade serous ovarian carcinoma
- HCC
- UPS and LMS.

Patients enrolled in Part A (Cohorts A1 through A6) will receive LY3435151 monotherapy. Patients enrolled in Part B (Cohorts B1 and B2) will receive LY3435151 and pembrolizumab.

The RP2D will be determined based on the number of observed dose-limiting toxicities (DLTs) and PK/pharmacodynamic (PD) data, and may be below the maximum tolerated dose (MTD), which may not necessarily be reached during the dose escalations. The dose-escalation phase will employ a modified toxicity probability interval (mTPI-2) method and starting with Cohort A2 will enroll at least three evaluable patients per cohort. Treatment cycles will consist of 21 days. A 2-cycle DLT observation will apply to all cohorts in Phase 1a. Refer to Section 4.1.1.1 for additional details on the dose escalation method.

A minimum of 1 patient will be enrolled in Cohort A1 and will receive a 10-mg dose. If the 10-mg dose level DLT period is cleared, Cohort A2 (30-mg dose level) will be initiated.

If a patient in Cohort A1 experiences a DLT, additional patients will be enrolled into Cohort A1 following the mTPI-2 method. Based on the mTPI-2 method, at least additional 4 patients will need to be enrolled and experience no DLT during the DLT observing period before escalating to the next dose level (Cohort A2).

After the first patient in Cohort A2 receives the first dose of LY3435151, there will be a delay of 1 week before the second patient receives LY3435151 to allow for safety observation. In all subsequent cohorts, the first patient in each dose level will be observed for at least 24 hours before treatment of additional patients; no additional delays are required for subsequent patients.

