4.1.1.1. Dose Escalation Method

Dose escalation of LY3435151 will be driven by an mTPI-2 method taking into consideration available safety, PK, and PD data from previous dose levels for Cohorts A2 through A6. A minimum of 3 evaluable patients will be enrolled in Cohorts A2 through A6.

Similar to the 3+3 design, the mTPI-2 method incorporates prespecified escalation rules. However, the mTPI-2 method is based on quantitative models that incorporate uncertainty into the decision rules, thereby allowing more precise RP2D selection. If 3 or 6 patients are enrolled in a cohort, the escalation rule parallels a traditional 3+3 design. However, it allows flexible number of patients in a cohort. For example, with 2 DLTs per 6 patients enrolled, the mTPI-2 would recommend staying at the current dose, as analogy to 1 DLT per 3 patients enrolled in 3+3 design; therefore, it allows more patients for a more precise estimate of the DLT rate at this dose level.

Following a discussion between the Lilly clinical research physician/clinical research scientist (CRP/CRS) and the investigators, a more conservative dose selection may be applied to the next cohort (for instance, if PK/PD data suggest that further dose increase would not be expected to yield additional benefit). For example, if the rule indicates “E” to escalate, the dose may stay at the current dose level or be de-escalated to a lower level, or escalation may cease. In the mTPI-2, the cohort size is not fixed. However, each cohort from Cohort A2 through A6 will contain a minimum of 3 evaluable patients, unless the escalation rules dictate that the dose should be de-escalated (“D” or “DU”). Doses can be escalated, de-escalated, and re-escalated. If the dose

decision was “DU,” the dose cannot be re-escalated to that level. This study is designed to identify a dose level with a dose-limiting target toxicity rate of 30%. The mTPI-2 method considers an equivalence interval around the target toxicity rate. For this study, the equivalence interval is elicited to be (25%, 35%), indicating that any values between 25% and 35% can be considered as accepted toxicity rates for MTD. The final MTD will be the dose for which the estimated toxicity rate is the closest to the target toxicity rate of 30% and less than 35%. The resulting mTPI-2 decision rules for any cohort size up to 20, and a hypothetical example for DLT determination after all patients complete DLT evaluations, are provided in Appendix 6.

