5.1.1. Dose Escalation Phase

Phase 1a (dose escalation) will assess the safety and tolerability of LY3435151 to identify a monotherapy RP2D and a combination RP2D in patients with solid tumors associated with TIL positivity:

- TNBC
- GC (including gastroesophageal junction)
- HNSCC
- squamous cervical carcinoma
- high-grade serous ovarian carcinoma
- HCC
- UPS and LMS

Patients enrolled in Part A (Cohorts A1 through A6) will receive LY3435151 monotherapy. Patients enrolled in Part B (Cohorts B1 and B2) will receive LY3435151 and pembrolizumab.

The RP2D will be determined based on the number of observed dose-limiting toxicities (DLTs) and PK/pharmacodynamic (PD) data, and may be below the maximum tolerated dose (MTD), which may not necessarily be reached during the dose escalations. The dose-escalation phase will employ a modified toxicity probability interval-2 (mTPI-2) method and, starting with Cohort A2, will enroll at least 3 evaluable patients per cohort. Treatment cycles will consist of 21 days. A 2-cycle DLT observation period (42 days) will apply to all cohorts in Phase 1a.

[figure not shown]
One patient will be enrolled in Cohort A1 and will receive a 10-mg dose on Cycle 1 Day 1. If the 10-mg dose level DLT period is cleared, Cohort A2 (30-mg dose level) will be initiated. If the patient in Cohort A1 experiences a DLT, additional patients will be enrolled into Cohort A1 following the mTPI-2 method. Based on the mTPI-2 method, at least 4 additional patients will need to be enrolled and experience no DLTs during the DLT observing period before escalating to the next dose level (Cohort A2).

After the first patient in Cohort A2 receives the first dose of LY3435151, there will be a delay of 1 week before the second patient receives LY3435151 to allow for safety observation. In all subsequent cohorts, the first patient in each dose level will be observed for at least 24 hours before treatment of additional patients; no additional delays are required for subsequent patients.

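### Appendix 6 reads the mTPI-2 grid by patients dosed but sets the MTD on DLT-evaluable patients, so a dosed patient who is not evaluable counts as event-free in escalation decisions

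*Protocol*

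**What the plan says.** Appendix 6 (Protocol 10.6) sets the column of the decision grid: "The number of patients dosed at a given dose level is shown in the columns (X-axis". It repeats patients dosed where it explains how to find the cell.

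For the MTD, the same appendix says its example is "based on the pre-specified parameters, number of DLTs, and number of DLT-evaluable patients", yet the denominator row of that example carries the label "of Patients Treated". Protocol 4.1.1.1 uses a further term: "with 2 DLTs per 6 patients enrolled, the mTPI-2 would recommend staying at the current dose". One quantity therefore has four labels: dosed, DLT-evaluable, treated and enrolled.

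Only DLT-evaluable is a defined dose-finding set (Protocol 9.3, SAP 5.4.1). A patient qualifies by completing 2 cycles with at least 75% of planned LY3435151 doses, or by stopping because of a DLT. Neither document says that this set enters the grid.

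Protocol 4.1.1 also sets a minimum: "starting with Cohort A2 will enroll at least three evaluable patients per cohort". For Cohort A1 the Protocol says "A minimum of 1 patient will be enrolled in Cohort A1" and the SAP says "One patient will be enrolled in Cohort A1 and will receive a 10-mg dose on Cycle 1 Day 1".

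**The concern.** A patient can be dosed, have no DLT and still not be DLT-evaluable. The documents give several routes:

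- radiotherapy needed in Cycles 1-2, which ends participation (Protocol 6.5.1);
- a potential DLT judged too confounded to use for dose selection (Protocol 4.1.1.2);
- more narrowly, a first Grade 3 infusion-related reaction that 4.1.1.2 exempts from the DLT definition, while the Grade 3 or 4 row in 6.6 permanently stops treatment. If LY3435151 stops in Cycle 1, the patient has at most 1 of 2 planned doses, or 50% against the required 75%.

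Such a patient was not observed for the full DLT period and so says little about the 42-day DLT risk. The look-up as written still adds the patient to the denominator as a non-event, which lowers the apparent DLT rate. The look-up drives escalation, so the stake is a dose increase, or a missed de-escalation, that the evaluable data do not support.

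**Working it through.** **Inputs.** Target 0.30 and equivalence interval 0.25 to 0.35 (Protocol 4.1.1.1). Stated calls: 1/3 S, 1/6 E, 2/3 D, 5/7 DU (Appendix 6) and 2/6 S (4.1.1.1). Not in the documents, so assumed: a Beta(1,1) prior, and DU when P(p > 0.30) exceeds 0.95. The full grid is a figure not available here, so cells beyond the stated calls are reconstructed.

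**Formula.** With x DLTs in n patients the posterior is Beta(1+x, 1+n-x). Each interval (a, b) of width 0.10 scores [F(b) - F(a)]/(b - a), and the highest score decides: below 0.25 is E, 0.25 to 0.35 is S, above 0.35 is D.

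**Reproduction.** All five stated calls are recovered. Applied to the example's counts, pooled rates of 0, 0, 0, 0.111, 0.111 and 0.667 return the stated MTD, dose level 5.

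**A change that needs no prior.** After one DLT in Cohort A1, Protocol 4.1.1 says "at least additional 4 patients will need to be enrolled and experience no DLT during the DLT observing period" before escalation. So 1 in 4 is not E, and 1 in 5 is the point at which escalation opens. Adding one non-evaluable patient to 1 DLT in 4 evaluable moves the look-up from the first cell to the second.

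**Changes on the rebuilt grid, one added patient.**

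| Evaluable count | Scores | Dosed count | Scores |
|---|---|---|---|
| 1/4: S | S 2.044, E 2.024 | 1/5: E | E 2.425, S 2.149 |
| 2/5: D | D 2.056, S 1.835 | 2/6: S | S 2.241, D 2.158 |

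These are the only changes among the 12 states with 3 to 6 evaluable patients and 0 to 2 DLTs. At 3 evaluable nothing changes (0/3 to 0/4 E, 1/3 to 1/4 S, 2/3 to 2/4 D, 3/3 to 3/4 DU). At 6 evaluable with 0 to 3 DLTs nothing changes either. Two added patients change 4 of the 12: 1/3 and 1/4 from S to E, and 2/4 and 2/5 from D to S. Over 3 to 12 evaluable patients and all DLT counts (85 states), one added patient changes 10, all permissively; 4 of these are DU to D and depend on the assumed cutoff.

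**Average effect.** Assume look-ups after every 3 evaluable patients, stopping at E, D or DU, with non-evaluable status independent of DLTs. At a true rate of 0.30 and at most 6 evaluable patients:

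- Evaluable count: 0/3 escalates, and 1/3 followed by 0/3 gives 1/6, which escalates. P(E) = 0.343 + 0.441 × 0.343 = 0.494.
- Dosed count with 10% non-evaluable: the extra patients per step are negative binomial, with P(0) = 0.729, P(1) = 0.2187, P(2 or more) = 0.0523 and P(3 or more) = 0.00856.
  - 1/3 with two or more extra escalates at once. Net gain: 0.441 × 0.0523 × (1 - 0.343) = 0.01515.
  - 2/6 with three or more extra in total escalates: 0.441 × 0.441 × (0.729 × 0.00856 + 0.2187 × 0.0523) = 0.00344.
  - 2/3 with three or more extra, then 0/3, escalates: 0.189 × 0.00856 × 0.343 = 0.00056.
  - Total: 0.49426 + 0.01515 + 0.00344 + 0.00056 = 0.513.

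The documents give no non-evaluable rate, so a range is shown (true DLT rate 30%):

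| Maximum evaluable | Evaluable count | Dosed, 2% | 5% | 10% | 20% |
|---|---|---|---|---|---|
| 6 | 0.494 | 0.495 | 0.499 | 0.513 | 0.567 |
| 12 | 0.561 | 0.568 | 0.578 | 0.596 | 0.645 |

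The cap of 6 is closer to the plan: the synopsis expects 18 to 22 patients over six Part A levels (3 to 3.7 each) and 6 to 8 over two Part B levels (3 to 4 each).

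**The case against.** The best defence is that patients dosed is loose labelling. Protocol 4.1.1.2 foresees cases set aside as non-evaluable for dose selection, and Protocol 9.5 and SAP 5.8 time the interim by patients deemed evaluable for assessing dose levels. Appendix 6 itself uses treated and DLT-evaluable for one count. There are also safeguards: a sponsor-investigator meeting after each cohort's DLT period (4.1.1), freedom to choose more conservatively (4.1.1.1), and an RP2D based on the totality of data (4.1.1.4).

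This shows the intent and limits the harm. It does not displace a look-up instruction stated twice. The evaluable minimum fixes how many such patients are needed, not which column to read, and the safeguards are discretionary.

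A reader might also infer more than the documents support:

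- **That the exempt infusion reaction is the main problem.** It needs a first Grade 3 reaction, no steroid prophylaxis, resolution within 6 hours and no recurrence, with LY3435151 stopped before the evaluability threshold is met. The discretionary DLT clause in 4.1.1.2 might also be invoked, although it sits badly with the explicit exclusion.
- **That Cohort A1 can be cleared on a non-evaluable patient.** Both documents open Cohort A2 only once the 10-mg DLT period is cleared, and the 2-cycle observation applies to every Phase 1a cohort. A patient stopped in Cycle 1 has not plainly cleared it. What remains is that this condition is not tied to the DLT-evaluable definition.
- **That cohorts of 3 are the most exposed.** One added patient changes no call there.

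**Conclusion.** The inconsistency is real, and the rule as written can err only towards a more permissive call. The clearest case, 1 in 4 becoming 1 in 5, rests on the Protocol's own text; 2 in 5 becoming 2 in 6 needs the reconstructed grid for its first cell. On average the effect is small: with at most 6 evaluable patients and a 30% true rate, it is 0.1 percentage points at 2% non-evaluable, 1.9 at 10% and 7.3 at 20%. Those averages rest on assumed non-evaluable rates and on look-ups at multiples of 3. Cohort size is not fixed, so a look-up at 4 or 5 evaluable patients, where a single patient matters, can occur and is not in the averages. The printed MTD example does not depend on the point: dropping one event-free patient at any level that has more than one patient leaves level 5 as the MTD.

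**What to change.** In Appendix 6, replace patients dosed with DLT-evaluable patients in both places. Relabel the denominator row of the MTD example and the 2-in-6 example in Protocol 4.1.1.1 to match, so that one denominator serves the look-up and the MTD. SAP 5.4.1 could state that this set enters the grid.

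Separately, reconcile these with the DLT-evaluable definition in Protocol 9.3 and SAP 5.4.1: the infusion-reaction exemption and discretionary clause in 4.1.1.2, the Grade 3 or 4 row in 6.6, and the condition for clearing Cohort A1 in Protocol 4.1.1 and SAP 5.1.1. How they are reconciled is for the clinical team.

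The cost is wording only, with no new procedures. An occasional non-evaluable patient may need replacing, which would slow escalation slightly.

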10.7. Appendix 7: Abbreviations

Term	Definition
ADA	antidrug antibody(ies)
AE	adverse event: Any untoward medical occurrence in a patient or clinical investigation participant administered a pharmaceutical product that does not necessarily have a causal relationship with this treatment. An AE can therefore be any unfavorable and unintended sign (including an abnormal laboratory finding), symptom, or disease temporally associated with the use of a medicinal (investigational) product, whether or not related to the medicinal (investigational) product.
ALP	alkaline phosphatase
ALT	alanine aminotransferase
ASCO	American Society of Clinical Oncology
AST	aspartate aminotransferase
AUC	area under the concentration-time curve
BED	biological effect dose
CFR	Code of Federal Regulations
CI	confidence interval
C_{max}	maximum concentration
CNS	central nervous system
complaint	A complaint is any written, electronic, or oral communication that alleges deficiencies related to the identity, quality, purity, durability, reliability, safety or effectiveness, or performance of a drug or drug delivery system.
compliance	Adherence to all study-related, good clinical practice (GCP), and applicable regulatory requirements.
CR	complete response
CrCl	creatinine clearance
CRF	case report form
CRP/CRS	clinical research physician/clinical research scientist: Individual responsible for the medical conduct of the study. Responsibilities of the CRP/CRS may be performed by a physician, clinical research scientist, global safety physician or other medical officer.
CSR	clinical study report
CT	computed tomography
CTLA-4	cytotoxic T-lymphocyte-associated protein 4
CTS	change in tumor size
CTCAE	Common Terminology Criteria for Adverse Events
DCR	disease control rate

DLT	dose-limiting toxicity
DVT	deep vein thrombosis
ECG	electrocardiogram
ECOG	Eastern Cooperative Oncology Group
eCRF	electronic case report form
EDC	electronic data capture
enroll	The act of assigning a participant to a treatment. Participants who are enrolled in the study are those who have been assigned to a treatment.
enter	Participants entered into a study are those who sign the informed consent form directly or through their legally acceptable representatives.
ERB	ethical review board
ET	equivalent toxicity
FDA	Food and Drug Administration
FSH	follicle-stimulating hormone
FT3	Free triiodothyronine
FT4	Free thyroxine
GCP	good clinical practice
G-CSF	granulocyte colony-stimulating factor
GLP	Good Laboratory Practice
GPS	Global Patient Safety
HCC	hepatocellular carcinoma
HER2	human epidermal growth factor receptor 2
HIV	human immunodeficiency virus
HNSCC	head and neck squamous cell carcinoma
HRT	hormonal replacement therapy
IB	Investigator's Brochure
ICF	informed consent form
ICH	International Council for Harmonisation
iCPD	confirmed progression per iRECIST
iCR	complete response per iRECIST
IEC	Independent Ethics Committee
Informed consent	A process by which a participant voluntarily confirms his or her willingness to participate in a particular study, after having been informed of all aspects of the study that are relevant to the participant's decision to participate. Informed consent is documented by means of a written, signed and dated informed consent form.

interim analysis	An interim analysis is an analysis of clinical study data, separated into treatment groups, that is conducted before the final reporting database is created/locked.
investigational product	A pharmaceutical form of an active ingredient or placebo being tested or used as a reference in a clinical trial, including products already on the market when used or assembled (formulated or packaged) in a way different from the authorized form, or marketed products used for an unauthorized indication, or marketed products used to gain further information about the authorized form.
IO	immuno-oncology
IP	intraperitoneal(ly)
iPR	partial response per iRECIST
irAE	immune-related adverse event
IRB	institutional review board
iRECIST	immuno-Response Evaluation Criteria in Solid Tumors
IRR	infusion-related reaction
iSD	stable disease per iRECIST
iUPD	unconfirmed progression per iRECIST
IV	intravenous(ly)
LMS	leiomyosarcoma
MedDRA	Medical Dictionary for Regulatory Activities
MTD	maximum tolerated dose
mTPI-2	modified toxicity probability interval
NL-NT	new lesion-non-target
NL-T	new lesion-target
ORR	overall response rate
PD	pharmacodynamic(s)
PD-1	programmed cell death protein 1
PD-L1	programmed death-ligand 1
PE	pulmonary embolism
PFS	progression-free survival
PK	pharmacokinetic(s)
PR	partial response
Q3W	every 3 weeks
QTc	corrected QT interval
RECIST	Response Evaluation Criteria in Solid Tumors
RNA	ribonucleic acid

RP2D	recommended phase 2 dose
SAE	serious adverse event
SAP	statistical analysis plan
screen	The act of determining if an individual meets minimum requirements to become part of a pool of potential candidates for participation in a clinical study.
SD	stable disease
SoA	Schedule of Activities
SOC	System Organ Class
SUSAR	suspected unexpected serious adverse reaction
T3	triiodothyronine
TBL	total bilirubin
TE-ADA	treatment-emergent antidrug antibody(ies)
TIL	tumor-infiltrating lymphocyte
TNBC	triple-negative breast cancer
TTR	time to response
ULN	upper limit of normal
UPS	undifferentiated pleomorphic sarcoma
WOCBP	woman/women of childbearing potential

